#### **6.1.4 Safety Population**

The Safety population will consist of all randomized subjects who have taken at least 1 dose of study treatment. The subjects in this group will be analyzed based on the treatment they received. Subjects who receive treatment from more than 1 arm will be assigned to the voclosporin arm.

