### **6.2.12 Randomization Strata**

The randomization will be stratified by biopsy class (Class V only versus Others) and by prior MMF use at time of screening. A regional blocking factor will also be used for supply purposes ensuring balance within region. The stratification factors and the regional blocking factor will be used as covariates in the primary analyses.

Tables of events or medications will be ordered in descending frequency of subjects followed by (where applicable) events for the higher level term (system organ class or ATC levels 4 and 2) followed by the preferred term. Ordering will be for the VCS treatment group first followed by the placebo group and alphabetical thereafter.

Listings will be sorted in the following order treatment group, subject, parameter, and visit unless otherwise stated. All data will be listed, subjects who were not randomized will be displayed after the randomized treatment groups.

Continuous variables will be summarized by the number of non-missing observations, mean, median, standard deviation, and minimum and maximum. For all tabulations of changes from baseline data, the lower and upper 95% confidence limits for the mean for the individual treatments will be given.

Categorical variables will be summarized by presenting the frequency and percent. Percentages will be based on the number of non-missing observations out of the subject population unless otherwise specified. For each variable, all categories will be shown. Zero frequencies (but not the percent) within a category will be presented.

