## 6.9 Exposure to Study Drugs

Overall exposure to study drugs (number of days of exposure to study drugs and mean dose) will be presented for both the Safety and ITT populations. Exposure will be based on prescribed dose. Exposure will not be summarized by visit but for the overall study duration. Overall study drug exposure will be calculated from the first dose date to the last dose date plus 1 for each prescribing record. Care should be taken to not double-count days. It is expected that prescription records will cover each study day between randomization and the end of study (or early termination). Periods of zero dose will be assigned as such.

The following gives an example of a subject with 4 prescription records over the 52-week (365 day) period.

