### 6.13.1 Adverse Events

A treatment emergent adverse event (TEAE) is defined as:

- Any AE that has an onset on or after the first dose of study drug up to last dose + 30 days. For subjects consenting to the AURORA 2 continuation study there will be an additional constraint to the TEAE definition: events must have an onset date prior to the first dose of AURORA 2 study drug.

A treatment-related TEAE is defined as a TEAE that is assessed by the Investigator or Sponsor as being related to study drug. If a TEAE has a missing relationship to study drug it is assumed to be related to the study drug for analysis purposes.

A disease-related TEAE is defined as a TEAE that is assessed by the Investigator or Sponsor as being related to the disease under study. If a TEAE has a missing relationship to the disease under study it is assumed to be related to the disease under study for analysis purposes.

Missing severity assessments will be summarised as severe.

The following tables will be presented for AEs:

- Summary table of overall incidence, the number of events, risk difference and 95% CI (voclosporin-placebo) including the following top line summaries:
  - Any AE
  - Any TEAE
  - Any Treatment-Related TEAE
  - Any Serious TEAE
  - Any Treatment-Related Serious TEAE
  - Any TEAE Leading to Voclosporin/Placebo Discontinuation
  - Any TEAE Leading to Death
  - Treatment-Related TEAE Leading to Death
  - Disease-Related TEAE
  - Disease-Related Serious TEAE

Detailed list of AE tables is given at the end of this SAP.

In counting the number of AEs reported, a continuous event (i.e., reported more than once and which did not cease), will be counted only once for a subject; a non-continuous AE reported several times by the same subject will be counted as multiple events.

Additional tables for serious TEAEs will be provided for each of the four regions: North America, Latin America, Europe/South Africa and Asia Pacific. Similar tables will also be provided for serious TEAEs occurring between day 1 and day 84 (Up to week 12), day 85 to day 168 (Week 12 to 24) and greater than day 168 (after week 24).

All AEs will be listed and a glossary of unique verbatim terms with coding information will be provided.

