#### **6.13.1.1 Exposure-adjusted incidence rates**

Additional tables of exposure-adjusted incidence rates (EAIR) for certain groups of adverse events will be provided. The exposure for a given preferred term will be calculated for each treatment group as the total time at risk of an event. Each subject will have their exposure ( $t_i$ ) calculated with the exposures being summed to generate an overall exposure ( $T$ ) for the event in question for each treatment group. Exposures will be calculated differently depending on whether the subject did or did not experience the event in question.

For subjects experiencing the event in question exposure is calculated as the number of days from first dose of study drug to the time of the event.

For subjects not experiencing the event in question exposure is calculated as the number of days from first dose to the end of the study.

Incidence rates (IR) for each preferred term are calculated within treatment group as the number of subjects ( $n$ ) experiencing the event divided by the total time at risk for all subjects in the treatment group. Exposure-adjusted incidence rates will be displayed as the number of events / 100 years of exposure. The difference (voclosporin minus placebo) between the exposure adjusted incidence rates along with a 95% CI for the difference will be reported for each preferred term using the normal approximation [3].

$$EAIR = \frac{n}{T} = \frac{n}{\sum t_i}$$

The test statistic is given by (v=voclosporin, p=placebo):

$$E = \left( \frac{n_v}{T_v} - \frac{n_p}{T_p} \right) / \sqrt{\frac{n_v}{T_v^2} + \frac{n_p}{T_p^2}}$$

The 95% CI for the difference in EAIR will be calculated as follows:

$$\left( \frac{n_v}{T_v} - \frac{n_p}{T_p} \right) - Z_{\alpha/2} \sqrt{\frac{n_v}{T_v^2} + \frac{n_p}{T_p^2}} \quad , \quad \left( \frac{n_v}{T_v} - \frac{n_p}{T_p} \right) + Z_{\alpha/2} \sqrt{\frac{n_v}{T_v^2} + \frac{n_p}{T_p^2}}$$

Using exposure adjusted incidence rates, the following tables will be provided:

- Treatment-Emergent Adverse Events by System Organ Class and Preferred Term using Exposure-Adjusted Incidence Rate [subjects (n), exposure and treatment comparisons]
- Serious Treatment-Emergent Adverse Events by System Organ Class and Preferred Term using Exposure-Adjusted Incidence Rate [subjects (n), exposure and treatment comparisons]

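### Serious TEAEs by period: the last period is 2.35 to 2.70 times as long as each of the others, and no denominator or person-time by period is stated

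*SAP*

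**What the plan says.** SAP Section 6.13.1 adds serious-TEAE tables by region, and similar ones for events "between day 1 and day 84 (Up to week 12), day 85 to day 168 (Week 12 to 24) and greater than day 168". The last period has no stated end. The TEAE definition in the same section supplies one: onset must fall "on or after the first dose of study drug up to last dose + 30 days", and for subjects entering the continuation study "events must have an onset date prior to the first dose of AURORA 2 study drug". Section 6.9 treats full treatment as a "52-week (365 day) period".

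Section 6.13.1 gives no denominator for the period tables. The general reporting conventions, printed after Section 6.2.12, say: "Percentages will be based on the number of non-missing observations out of the subject population unless otherwise specified". The Safety population is "all randomized subjects who have taken at least 1 dose of study treatment" (Section 6.1.4). Section 6.13.1 adds: "Detailed list of AE tables is given at the end of this SAP". In the public text Section 11 shows only its heading, so any denominator set there cannot be seen.

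Section 6.13.1.1 states: "Additional tables of exposure-adjusted incidence rates (EAIR) for certain groups of adverse events will be provided". One of these covers serious TEAEs, with a treatment difference and CI, but over the whole study and without a split by period. For subjects without the event, exposure there runs from first dose to study end.

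**The concern.** These are the only serious-TEAE summaries by time on treatment that the available text describes. Their timing will draw attention, because Protocol Section 1.2.4.2 reports 10 deaths on low-dose voclosporin against 1 on placebo in Phase 2.

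There are two separate difficulties.

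- **Across periods.** The late window is longer, so a crude percentage can rise after Day 168 with no change in hazard.
- **Between arms, late period.** Subjects who stop study drug are expected to stay in the study (Protocol Section 5.6). Once more than 30 days past their last dose they can no longer have a TEAE. If the denominator is everyone dosed, they still count. The arm with more stopping then shows a lower late percentage at the same on-treatment hazard.

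Unequal stopping is plausible. In Phase 2, decreased GFR led to permanent discontinuation in 1.1% of placebo and 6.7% of low-dose subjects (Protocol Section 1.2.5).

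**Working it through.** **Period lengths.** The SAP's boundaries reproduce: 12 × 7 = 84 and 24 × 7 = 168.

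- First period: 84 days. Second period: 168 − 84 = 84 days.
- Third period, ending Day 365 (direct entry to the continuation study, assumed): 365 − 168 = 197 days; 197/84 = 2.35.
- Third period, ending at last dose + 30 for a Day 365 completer: 395 − 168 = 227 days; 227/84 = 2.70.

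**Crude percentages with no change in hazard.** Assume a 20% one-year risk, a constant hazard, no dropout and everyone dosed as denominator.

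- Hazard: λ = −ln(1 − 0.20)/365 = 0.000611 per day.
- Share with at least one event in a period of L days: 1 − exp(−λL).

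| Period | L (days) | Share |
|---|---|---|
| Days 1-84 | 84 | 5.0% |
| Days 85-168 | 84 | 5.0% |
| After Day 168, to Day 365 | 197 | 11.3% |
| After Day 168, to Day 395 | 227 | 13.0% |

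The late/early ratio is 2.27 to 2.59. The Phase 2 SAE figures in Protocol Section 1.2.4.2 (25.8% low dose, 15.8% placebo) do not clearly state the period covered. Read as either 168-day or 365-day incidence, they give ratios of 2.13 to 2.61. If only a subject's first event counts, the range is 1.58 to 2.42.

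**Effect of discontinuation on the ratio.** The documents give no expected rate, so a range is assumed. Let a fraction d stop by Day 365 at a constant rate μ = −ln(1 − d)/365, with risk continuing for 30 days after the last dose. The share at risk is 1 to Day 30 and exp(−μ(t − 30)) afterwards. Person-time in the last period divided by that in the first is:

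| d by Day 365 | Ending Day 365 | Ending Day 395 |
|---|---|---|
| 0% | 2.35 | 2.70 |
| 10% | 2.20 | 2.53 |
| 20% | 2.05 | 2.34 |
| 25% | 1.98 | 2.25 |
| 30% | 1.90 | 2.15 |
| 40% | 1.73 | 1.96 |

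The ratio falls below 2 once the mean share at risk in the last period is under 168/197 = 85% (ending Day 365) or 168/227 = 74% (ending Day 395).

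**Arm comparison in the last period.** Assume that 20% of one arm and 30% of the other are outside the TEAE window by Day 168, nobody stops later, hazards are equal, and the period ends at Day 365. Then 11.35% × 0.80 = 9.08% and 11.35% × 0.70 = 7.94%, a spurious difference of about 1.1 points. With 162 per arm, that is 162 × 0.0113 = 1.8 subjects.

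**After the change.** With person-time in each period as denominator, a constant hazard gives the same rate in all three periods. For example, it is 29.9 per 100 patient-years if the 25.8% is read as 365-day incidence.

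**The case against.** The strongest reply is that these are descriptive tables with explicit day labels, and no test or decision rests on them. Discontinuation of study drug is tabulated by arm and visit (SAP Section 6.4). All AEs are listed, and Protocol Section 13.9 summarises SAEs from consent onward, not only TEAEs. A whole-study exposure-adjusted table is also planned. All of this stands, and it keeps the severity low. It does not supply a rate by period.

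The whole-study exposure-adjusted table does not fill the gap. It has no time split, and for event-free subjects it counts time to the end of the study, including time when a TEAE is no longer possible.

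Three stronger readings are tempting, but the documents do not support them.

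- A reader might infer that the SAP fixes the denominator at everyone dosed. It does not say so for these tables. That follows only from the general default, and the table list could override it.
- A reader might infer that the late percentage must be more than twice the early one. That needs a roughly constant hazard and little dropout. A falling hazard or more stopping lowers the ratio, and counting only first events lowers it too.
- A reader might infer that the long last period hides an early excess on voclosporin. It cannot: an arm difference in Days 1-84 appears in its own table, and both arms share the same boundaries.

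**Conclusion.** The point holds in limited form. The last period is 2.35 to 2.70 times as long as each of the two equal earlier ones, its end is unstated, and no denominator or exposure adjustment by period is given. Only the lengths rest on the SAP's own figures, with direct rollover or last dose + 30 days as the two end points.

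Under the default denominator, crude percentages should not be compared across periods as if they were rates. The size of the apparent late rise depends on the assumed hazard and on discontinuation, for which the documents give no rate.

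The between-arm distortion is possible only if stopping, or entry to the continuation study, differs between arms. The 1.1 points rests wholly on the assumed 20% v 30%. Unequal period length by itself leaves the within-period arm comparison unbiased.

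This is a cheap improvement to descriptive safety tables, of low severity.

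**What to change.** In SAP Section 6.13.1:

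1. State that the last period ends when the TEAE window closes: last dose + 30 days, or the first continuation-study dose if earlier.
2. Use as the denominator for each period the subjects still in the TEAE window at its start.
3. Add, by arm and period, the number of subjects with an event, person-time, and rate per 100 patient-years, with the difference and CI formula of Section 6.13.1.1.
4. Define person-time within the period. A subject with an event counts to the first event in that period. An event-free subject counts to the earliest of the period end, the close of the TEAE window, death or study exit.

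Step 4 matters because reusing the exposure rule of Section 6.13.1.1 unchanged would count event-free subjects to study end and bring the dilution back. Step 2 alone does not make periods of different length comparable; the person-time rate does that, so the period boundaries can stay as they are.

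The cost is a few lines of SAP text and a small amount of extra programming. No new data are needed.

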#### **6.13.1.1 Exposure-adjusted incidence rates**

Additional tables of exposure-adjusted incidence rates (EAIR) for certain groups of adverse events will be provided. The exposure for a given preferred term will be calculated for each treatment group as the total time at risk of an event. Each subject will have their exposure ( $t_i$ ) calculated with the exposures being summed to generate an overall exposure ( $T$ ) for the event in question for each treatment group. Exposures will be calculated differently depending on whether the subject did or did not experience the event in question.

For subjects experiencing the event in question exposure is calculated as the number of days from first dose of study drug to the time of the event.

For subjects not experiencing the event in question exposure is calculated as the number of days from first dose to the end of the study.

Incidence rates (IR) for each preferred term are calculated within treatment group as the number of subjects ( $n$ ) experiencing the event divided by the total time at risk for all subjects in the treatment group. Exposure-adjusted incidence rates will be displayed as the number of events / 100 years of exposure. The difference (voclosporin minus placebo) between the exposure adjusted incidence rates along with a 95% CI for the difference will be reported for each preferred term using the normal approximation [3].

$$EAIR = \frac{n}{T} = \frac{n}{\sum t_i}$$

The test statistic is given by (v=voclosporin, p=placebo):

$$E = \left( \frac{n_v}{T_v} - \frac{n_p}{T_p} \right) / \sqrt{\frac{n_v}{T_v^2} + \frac{n_p}{T_p^2}}$$

The 95% CI for the difference in EAIR will be calculated as follows:

$$\left( \frac{n_v}{T_v} - \frac{n_p}{T_p} \right) - Z_{\alpha/2} \sqrt{\frac{n_v}{T_v^2} + \frac{n_p}{T_p^2}} \quad , \quad \left( \frac{n_v}{T_v} - \frac{n_p}{T_p} \right) + Z_{\alpha/2} \sqrt{\frac{n_v}{T_v^2} + \frac{n_p}{T_p^2}}$$

Using exposure adjusted incidence rates, the following tables will be provided:

- Treatment-Emergent Adverse Events by System Organ Class and Preferred Term using Exposure-Adjusted Incidence Rate [subjects (n), exposure and treatment comparisons]
- Serious Treatment-Emergent Adverse Events by System Organ Class and Preferred Term using Exposure-Adjusted Incidence Rate [subjects (n), exposure and treatment comparisons]

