Procedures:	
See Schedule of Events for full details of protocol required procedures and applicable visits (and timings). Subjects who have provided signed and dated informed consent will be screened for entry into this study. Baseline proteinuria level is determined by a mean of 2 first morning void urine samples taken during the screening period. If a subject has not had a kidney biopsy within the required timeframe for study eligibility, one may be performed to assess eligibility into the study, provided consent is in place and provided the results are received before randomization. Subjects meeting the required eligibility criteria will be randomized in a ratio of 1:1 to receive either Orelvo (23.7 mg BID) or matching placebo starting on Day 1. All subjects will receive initial treatment with 0.5 to 1.0 g IV methylprednisolone. In consultation with the Medical Monitor, and if it is in the subject's best interest, IV methylprednisolone may be started during the screening period. Subjects receiving IV methylprednisolone in the 3 months prior to screening must be discussed with the Medical Monitor prior to initiating further IV methylprednisolone. For subjects who are not already taking prescribed MMF prior to randomization, the dosing of MMF will start at 500 mg BID for a total daily dose of 1 g/day for the first week, increasing to 1 g BID for a total daily dose of 2 g/day for the second and subsequent weeks (i.e., beginning on Day 8).
 
All subjects will complete dosing through 52 weeks of study treatment. Subjects who permanently discontinue study treatment before the Week 52 visit will return for all remaining study visits and assessments unless they have withdrawn consent. All subjects who complete participation and study treatment through 52 weeks and provide consent will have the opportunity to enroll into a continuation study for which the details are not yet finalized.

Sample Size:	
A 2 group continuity corrected Chi square test with a 0.05 two-sided significance level will have 80% power to detect the difference between a placebo response rate of 20.0% and an Orelvo response rate of 34.4% (odds ratio=2.1) when the sample size in each group is 162 (total N=324). While the effect of withdrawals will be investigated, subjects withdrawing for any reason will be counted as non-responders in the primary analysis and therefore no adjustment of sample size for withdrawals is necessary.

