Notes: Subjects who discontinue therapy will attend their regularly scheduled study visits to the end of the study. Subjects who withdraw consent and terminate the study early or discontinue treatment early should be advised to attend both Visit 17 and the Safety Follow up Visit (Visit 18).

Abbreviations: AE=adverse event; BP=blood pressure; CBC=complete blood count; ECG=electrocardiogram; FMV=first morning void; HRQoL=health-related quality of life; IV=intravenous; LN=lupus nephritis; MMF=mycophenolate mofetil; QTcF=QT interval duration corrected for heart rate using method of Fridericia; SAE=serious adverse event; SELENA-SLEDAI=Safety of Estrogens in Lupus Erythematosus National Assessment - Systemic Lupus Erythematosus Disease Activity Index; SLE=systemic lupus erythematosus.

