### 3 ENDPOINTS

#### 3.1 Primary Endpoint

Renal response at Week 52 will be adjudicated by the Clinical Endpoints Committee (CEC) based on the following parameters:

- UPCR of  $\leq 0.5$  mg/mg, and
- eGFR  $\geq 60$  mL/min/1.73 m^2 or no confirmed decrease from baseline in eGFR of  $>20\%$ , and
- Received no rescue medication for LN (see Protocol Section 7.8, Prohibited Therapy and Concomitant Treatment), and
- Did not receive more than 10 mg prednisone for  $\geq 3$  consecutive days or for  $\geq 7$  days in total during Weeks 44 through 52, just prior to the renal response assessment

The CEC will also take into account the following:

- Subjects who withdraw from the study prior to the Week 52 assessment and provide insufficient week 52 data to determine response will be defined as non-responders. Subjects who discontinue study drug but continue to attend study visits (as is the expectation) will have their data assessed for response.
- eGFR values eliminating a subject from complete remission should be accompanied by a treatment or disease-related treatment-emergent adverse event (TEAE) that impacts eGFR. Full details are given in Section [6.11.1](#).
- The CEC is independent and blinded from the treatment groups.

The primary endpoint estimand is the proportion of subjects showing renal response as adjudicated by the CEC in the ITT population when comparing voclosporin and placebo at Week 52. It is assessed in all randomized subjects who were recruited according to the inclusion/exclusion criteria of the protocol.

The variable is binary and indicates a response if a subject shows, at 1 year, adequate UPCR with no signs of detrimental impact on eGFR. Subjects who cannot be shown to be responders through their 1 year data (or absence thereof) are defined as non-responders.

Intercurrent events include:

- Treatment discontinuation for any reason
  - the subject remains on study, allowing the primary endpoint to be assessed at 1 year.
- Study discontinuation
  - resulting in insufficient information at 1 year to ascertain response status leading to assumed non-response.
- Rescue medication taken at any time prior to the primary assessment at 1 year
  - results in non-response. Rescue medication is adjudicated by the Clinical Endpoints Committee.
- Death at any time prior to the 1 year primary assessment
  - results in assumed non-response.

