## **7 INTERIM ANALYSIS**

There are no planned interim analyses. The analysis of the primary endpoint (renal response at Week 52) will be conducted at the end of the study.

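### Exposure-adjusted incidence rates count TEAEs only to last dose + 30 days but run event-free time to an undefined end of the study, so numerator and denominator cover different windows

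*SAP*

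**What the plan says.** **Numerator.** Both EAIR tables listed in SAP 6.13.1.1 are TEAE tables. SAP 6.13.1 defines a TEAE as "Any AE that has an onset on or after the first dose of study drug up to last dose + 30 days". For subjects entering the continuation study it adds that "events must have an onset date prior to the first dose of AURORA 2 study drug".

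**Denominator.** SAP 6.13.1.1 describes exposure as the time a treatment group spends at risk of the event. A subject with the event contributes time to the event. For the rest, "For subjects not experiencing the event in question exposure is calculated as the number of days from first dose to the end of the study". Neither limit on the numerator is repeated here.

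**Follow-up after stopping drug.** The notes to SAP Table 1.1 say: "Subjects who discontinue therapy will attend their regularly scheduled study visits to the end of the study". The Protocol Synopsis says that such subjects "will return for all remaining study visits and assessments unless they have withdrawn consent". SAP 3.1 treats this as the normal course: "Subjects who discontinue study drug but continue to attend study visits (as is the expectation) will have their data assessed for response".

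**Meaning of the end date.** The text available gives no subject-level date for this purpose, and the phrase is used in several ways:
- In the Table 1.1 notes it is the last regular visit of subjects off therapy.
- In SAP 6.9 it is paired with early termination: "It is expected that prescription records will cover each study day between randomization and the end of study (or early termination".
- In Protocol 9.2.3 it labels Visit 15, which may be early.
- In SAP 7 it is the end of the trial: "The analysis of the primary endpoint (renal response at Week 52) will be conducted at the end of the study".

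**The concern.** A rate per 100 years estimates a hazard only if every day in the denominator is a day on which an event could have been counted. Here there are two mismatches, and they act in opposite directions.

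1. A subject who stops drug and stays on study has a TEAE window that closes 30 days after the last dose, while the event-free clock keeps running. This lowers the rate.
2. If the end is Week 52, a completer who does not roll over can still have TEAEs counted up to Visit 16, about 28 days after the event-free clock has stopped. This raises the rate. If the end is an early Visit 15, stoppers have the same upward effect.

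The tables report a between-arm difference with a 95% CI for each preferred term. Under a Week 52 end, the arm with more stopping has its rate diluted more. If that is the voclosporin arm, an excess of harm is understated. Two programmers who read the end date differently would also obtain different rates from the same data.

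The amendment log places the EAIR tables in version 2.0 and the 30-day limit in version 5.0. That may explain how the windows came apart; the concern rests only on the current text.

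**Working it through.** The plan states no EAIR figure, so there is none to reproduce. The check compares the SAP rule with a window-matched rule.

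**Inputs from the documents:** TEAE window to last dose + 30 days, cut at the first AURORA 2 dose (SAP 6.13.1); Visit 16 at 4 weeks after last dose (SAP Table 1.1, footnote 3); 162 per arm (SAP 4); Phase 2 stopping for GFR-decrease TEAEs of 6.7% at 23.7 mg BID versus 1.1% on placebo (Protocol 1.2.5). These last shares are for one cause of stopping only.

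**Assumptions, because the documents give no overall stopping, rollover or event rates:** true rate 20 per 100 years, constant inside the TEAE window; stop days even over 52 weeks; stoppers followed to day 364; stopping 6.7% to 40%; none, half or all completers roll over.

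**Single-subject windows, event-free, Week 52 end (day 364):**
- Stop at day 84: window closes at day 84 + 30 = 114; excess time 364 − 114 = 250 days.
- Stop at day 182: window closes at day 212; excess 152 days.
- Averaged over stop days: 334² / (2 × 364) = 153 days.
- Completer without rollover: events counted to Visit 16 at day 392; event-free time is 28 days short.

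**Formula.** Let λ be the rate, w the countable window and e the event-free end. Each subject contributes expected events 1 − exp(−λw) and expected time (1 − exp(−λw))/λ + (e − w)·exp(−λw). If e = w for everyone, events divided by time equals λ exactly, whatever the stopping or rollover. All error comes from e − w.

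**Worked example: 30% stopping, full rollover, Week 52 end, λ = 0.20 per year.**
- Completer: w = e = 364 days; events 1 − exp(−0.20 × 364/365.25) = 0.1807; time 0.1807/0.20 = 0.9036 years.
- Stopper, averaged over stop days: events 0.1076; time 0.9264 years.
- Arm events: 162 × (0.3 × 0.1076 + 0.7 × 0.1807) = 25.72.
- Arm time: 162 × (0.3 × 0.9264 + 0.7 × 0.9036) = 147.49 years.
- EAIR = 100 × 25.72/147.49 = 17.44; ratio to truth 17.44/20 = 0.872.

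**SAP rate divided by true rate, Week 52 end:**

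| Stopping | All roll over | Half | None |
|---|---|---|---|
| 6.7% | 0.971 | 1.003 | 1.035 |
| 10% | 0.957 | 0.988 | 1.019 |
| 20% | 0.915 | 0.942 | 0.969 |
| 30% | 0.872 | 0.896 | 0.920 |
| 40% | 0.830 | 0.851 | 0.871 |

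The sign changes at about 7% stopping if half of completers do not roll over, and at about 14% if none do.

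**Other readings of the end date:**
- Subject's own last contact: 0.971–0.973 at 6.7% stopping and 0.830–0.837 at 40%.
- Early Visit 15: 1.006 to 1.040 with full rollover, 1.072 to 1.091 with none.
- Visit 16 at 4 weeks after last dose for all who do not roll over: error only +0.1% to +0.6%. This was run under a separate set of assumptions: 10–30% stopping at day 91 or 182, rates of 5 and 50 per 100 years.

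**Between arms, Week 52 end**, with the SAP's SE = 100 × √(n_v/T_v² + n_p/T_p²):
- Equal true rates, stopping 6.7% versus 1.1%: false difference −0.48, −0.52 or −0.56 at 0%, 50% or 100% non-rollover (SE 5.18, 5.27, 5.35), about 0.1 SE.
- Equal true rates, 30% versus 20%: with full rollover 17.44 − 18.29 = −0.85 (SE 4.93, 0.17 SE); with no rollover −0.99 (0.20 SE).
- True 25 versus 20, 30% versus 20%, full rollover: 100 × 31.43/144.27 = 21.79, less 100 × 26.91/147.12 = 18.29, gives 3.50 (SE 5.25). The shortfall is (5.0 − 3.5)/5.25, about 0.3 SE. With no rollover the difference is about 3.6.
- True 25 versus 20, 20% in both arms: reads 4.6 with full rollover (4.80 with none). With full rollover, difference/SE is 0.858 against 0.859 when the windows match.

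**The case against.** **Text not in the copy reviewed.** The SAP contents list a section 6.2.15 on adverse events whose text is not in the copy reviewed, and an end date may be given there. That stands as a caveat. Such a date would settle the ambiguity, but it would remove the mismatch only if it followed the TEAE window.

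**A sensible reading nearly closes the gap.** Protocol 10.3.1 ends AE reporting at Visit 15 for rollover subjects and at Visit 16 otherwise. Protocol 9.2.4 places Visit 16 four weeks after last dose, including for those who stop early. Protocol 10.3.2 ends routine SAE reporting 30 days after last dose for those who discontinue. Read that way, the error is well under 1%. This is the strongest point, but SAP 6.13.1.1 names none of these dates, and the plan expects stoppers to keep attending after Visit 16 would have taken place.

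**Not every use of the phrase is a rival definition.** SAP 7 describes when the analysis is run, not when a subject's exposure ends. That is fair; the ambiguity lies mainly between Week 52, Visit 15 and Visit 16.

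**The effect is small.** The only stopping shares in the documents move the difference by about 0.1 SE, the larger shares are assumed, and these are additional tables. That is right, and it fixes the severity.

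**Conclusion.** The concern holds as a minor error in the rule as written. The numerator is capped and the denominator is not, although the SAP itself describes exposure as time at risk. The direction is not fixed. Under a Week 52 end, the ratio of the SAP rate to the true rate runs from 0.83 (40% stopping, full rollover) to 1.035 (6.7% stopping, no rollover); an early Visit 15 end gives up to 1.091. The between-arm comparison is distorted mainly when stopping differs by arm: about 0.1 SE at the Phase 2 shares, and about 0.3 SE for a true difference of 5.0 at 30% versus 20% stopping.

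These sizes depend on the assumed event rate, stop times, stopping and rollover; the mismatch itself does not. Confidence is medium because SAP 6.2.15 could not be read. The crude AE tables with risk differences, and all efficacy analyses, are unaffected.

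**What to change.** In SAP 6.13.1.1, state that a subject without the event contributes time from first dose to the earliest of last dose + 30 days, first AURORA 2 dose, death and the subject's own last study contact. Under the assumptions above this returns the true rate at any level of stopping or rollover.

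If on-study rates are also wanted, add a separate table that pairs all AEs from first dose to a defined subject-level end of study with time to that same date.

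The cost is one sentence and one derivation change. Last-dose dates are already collected, and SAP 6.2.7 and 6.9 already cover missing ones. If SAP 6.2.15 holds an end date, bring it into line with the same rule.
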